# Appendix C: List of preferred terms defining the safety topics of interest

The PTs are based on MedDRA version 23.1 and these will be updated with the current MedDRA version for consistency.

# **Hypotension**

- Hypotension
- Diastolic hypotension
- Orthostatic hypotension

# **Deteriorating renal function**

- Acute kidney injury
- Acute phosphate nephropathy
- Anuria
- Azotaemia
- Continuous haemodiafiltration
- Dialysis
- Foetal renal impairment
- Haemodialysis
- Haemofiltration
- Neonatal anuria
- Nephropathy toxic
- Oliguria
- Peritoneal dialysis
- Prerenal failure
- Renal failure
- Renal failure neonatal
- Renal impairment
- Renal impairment neonatal
- Subacute kidney injury

TP-GDO-WW-016-08 CONFIDENTIAL Effective Date: 26 Nov 19 Project Document Effective Date: Date of last signature Related to: SOP-GDO-WW-019

Page 50 of 50

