5.1 Inclusion Criteria

Participants are eligible to be included in the study only if all of the following criteria apply at screening (Visit 1a):

Age

1 Participant must be 21 years of age or older, at the time of signing the informed consent.

Type of Participant and Disease Characteristics

- 2 Documented diagnosis of stable symptomatic HF (NYHA class II-III) at screening (Visit 1a), and a medical history of typical symptoms and signs of HF in those who are currently receiving loop diuretic treatment.
 - Typical symptoms associated with HF: breathlessness, orthopnoea, paroxysmal nocturnal dyspnoea, reduced exercise tolerance, fatigue, tiredness, increased time to recover after exercise.
 - Signs associated with HF:
 - More specific: elevated jugular venous pressure, hepatojugular reflex, third heart sound (gallop rhythm), laterally displaced apical impulse.
 - Less specific: weight gain (> 2 kg/week), weight loss (in advanced HF), tissue wasting (cachexia), cardiac murmur, peripheral oedema (ankle, sacral, scrotal), pulmonary crepitations, reduced air entry and dullness to percussion at lung bases (pleural effusion), tachycardia, irregular pulse, tachypnoea, Cheyne Stokes respiration, hepatomegaly, ascites, cold extremities, oliguria, narrow pulse pressure.
- Left ventricular ejection fraction < 60% documented by the most recent echocardiogram
 2D or 3D or cardiac magnetic resonance imaging within the last 12 months prior to screening.

If patient has experienced an acute myocardial event/injury associated with release of cardiac troponin within the previous 12 months, then a more recent echocardiogram to determine eligibility for participation in the study must be at least 12 weeks after the most recent cardiac event.

4 Patients should be treated for HF, hypertension, T2DM, or renal disease according to guidelines.

Note: Background treatment should be in line with locally recognised treatment guidelines in each indication, as described in Section 6.5.2. Both patients with or without SGLT2i treatment can be included in the study (Section 6.1.1).

- 5 NT-proBNP ≥ 300 pg/mL for patients with sinus rhythm at screening; and NT proBNP ≥ 600 pg/mL for patients with atrial fibrillation/flutter at screening, using local laboratory sample.
- 6 eGFR \ge 30 and \le 60 mL/min/1.73 m² (by CKD-EPI formula based on local laboratory sample).

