8.3.5 Adverse Events Based on Examinations and Tests

The results from the protocol-mandated laboratory tests and vital signs will be summarised in the CSR.

Deterioration as compared to baseline in protocol-mandated laboratory values, vital signs, ECG parameters and echocardiography findings should therefore only be reported as AEs if they fulfil any of the SAE criteria, are the reason for discontinuation of treatment with the investigational product or are considered to be clinically relevant as judged by the investigator (which may include but not limited to consideration as to whether treatment or non-planned visits were required or other action was taken with the study treatment, eg, dose adjustment or drug interruption).

If deterioration in a laboratory value/vital sign is associated with clinical signs and symptoms, the sign or symptom will be reported as an AE and the associated laboratory result/vital sign will be considered as additional information. Wherever possible the reporting investigator uses the clinical, rather than the laboratory term (eg, anaemia versus low haemoglobin value). In the absence of clinical signs or symptoms, clinically relevant deteriorations in non-mandated parameters should be reported as AE(s).

Any new or aggravated clinically relevant abnormal medical finding at a physical examination as compared with the baseline assessment will be reported as an AE.

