Appendix B Adverse Events: Definitions and Procedures for Recording, Evaluating, Follow-up, and Reporting

B1 Definition of Adverse Events

An AE is the development of any untoward medical occurrence in a participant or clinical study participant administered a medicinal product and which does not necessarily have a causal relationship with this treatment. An AE can therefore be any unfavourable and unintended sign (eg, an abnormal laboratory finding), symptom (for example nausea, chest pain), or disease temporally associated with the use of a medicinal product, whether or not considered related to the medicinal product.

The term AE is used to include both serious and non-serious AEs and can include a deterioration of a pre-existing medical occurrence. An AE may occur at any time, including run-in or washout periods, even if no study treatment has been administered.

B 2 Definitions of Serious Adverse Event

A SAE is an AE occurring during any study period (ie, run-in, treatment, washout, follow-up), that fulfils one or more of the following criteria:

- Results in death
- Is immediately life-threatening
- Requires in-participant hospitalisation or prolongation of existing hospitalisation
- Results in persistent or significant disability or incapacity
- Is a congenital anomaly or birth defect
- Is an important medical event that may jeopardise the participant or may require medical treatment to prevent one of the outcomes listed above

Adverse events for **malignant tumours** reported during a study should generally be assessed as **serious** AEs. If no other seriousness criteria apply, the 'Important Medical Event' criterion should be used. In certain situations, however, medical judgement on an individual event basis should be applied to clarify that the malignant tumour event should be assessed and reported as a **non-serious** AE. For example, if the tumour is included as medical history and progression occurs during the study, but the progression does not change treatment and/or prognosis of the malignant tumour, the AE may not fulfil the attributes for being assessed as serious, although reporting of the progression of the malignant tumour as an AE is valid and should occur. Also, some types of malignant tumours, which do not spread remotely after a routine treatment that does not require hospitalisation, may be assessed as non-serious; examples in adults include Stage 1 basal cell carcinoma and Stage 1A1 cervical cancer removed via cone biopsy.

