# **Deteriorating renal function**

Deteriorating renal function will be evaluated by analysis of serum creatinine and eGFR values (percent change from baseline in eGFR, absolute values and change from baseline, values meeting protocol-defined discontinuation criteria for deteriorating renal function) and analysis of pre-defined AE preferred terms related to deteriorating renal function.

Deteriorating renal function will be presented as:

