#### **Deteriorating renal function monitoring over time**

Absolute value, change and percentage change from baseline in eGFR (central labs) by visit and treatment

SToI analysis of PTs as described in Appendix C: List of preferred termsC: List of preferred terms. This would include an overall summary table of frequencies of AE, SAEs, DAEs, and a summary table by PT based on a pre-defined list of preferred terms

TP-GDO-WW-016-08 **CONFIDENTIAL** Effective Date: 26 Nov 19 **Project Document Effective Date**: Date of last signature Related to: SOP-GDO-WW-019

The summary will be provided for all the AE with an onset date, or worsening, on or after first dose of investigational medical product (IMP) and within 28 days after last dose of IMP and based on the on-treatment definition when otherwise specified. A summary based by eGFR categories will be also presented.

The incidence of hyperkalaemia, hypotension and deteriorating renal function will be summarized by treatment group.

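### The renal adverse-event list in SAP Appendix C has no term for a fall in eGFR, a rise in creatinine or worsening chronic kidney disease, so the renal AE/SAE/DAE tables can undercount

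*SAP*

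**What the plan says.** Deteriorating renal function is one of three safety topics of interest in SAP 4.11.3. Part of its evaluation is an "analysis of pre-defined AE preferred terms related to deteriorating renal function". The SAP then describes the output: "This would include an overall summary table of frequencies of AE, SAEs, DAEs, and a summary table by PT based on a pre-defined list". The list is in Appendix C, under Deteriorating renal function, and runs alphabetically from "Acute kidney injury" to "Subacute kidney injury", with terms such as "Foetal renal impairment" between them. The introduction to Appendix C says that the terms will be brought into line with the current MedDRA version; it mentions no other revision.

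Three parts of the protocol decide which renal events become AEs:

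- Section 7.1 and Appendix F 2 define the mandatory renal stop by eGFR alone: a confirmed fall of more than 50% from baseline and/or a confirmed value below 15 mL/min/1.73 m².
- Section 8.3.5 makes deterioration in a protocol-mandated laboratory value reportable as an AE if it meets an SAE criterion, if it is among those that "are the reason for discontinuation of treatment with the investigational product", or if the investigator judges it clinically relevant. It prefers the clinical to the laboratory term where that can be done.
- Appendix B 1 says that an AE "can include a deterioration of a pre-existing medical occurrence". The trial enrols patients with heart failure and CKD (section 4.1).

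**The concern.** The protocol describes this risk in terms of eGFR. Table 2 of the protocol couples deteriorating renal function with an initial eGFR decrease and notes that MRA treatment in heart failure and the SGLT2 inhibitor class are both associated with an early modest decrease. In patients who already have CKD, an investigator who stops drug under the eGFR rule could naturally record the AE as a fall in eGFR, a rise in creatinine or a worsening of CKD. If those wordings match nothing on the list, the renal AE/SAE/DAE tables omit the kind of event that the safety topic was set up to follow.

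The DAE count is the most exposed, because the event that forces discontinuation is a laboratory value. A reader could then find a renal DAE table that disagrees with the CRF-based count of renal discontinuations, with nothing in the report to explain the gap.

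**Working it through.** No formula applies and the SAP states no figure to reproduce. The check is a count of the list, followed by a comparison of the outputs that could hold such an event.

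**Step 1: classify the Appendix C renal list.**

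| Group | Terms | Count |
|---|---|---|
| Renal failure, impairment, injury or toxicity | Acute kidney injury, acute phosphate nephropathy, nephropathy toxic, prerenal failure, renal failure, renal impairment, subacute kidney injury | 7 |
| Dialysis or filtration procedures | Continuous haemodiafiltration, dialysis, haemodialysis, haemofiltration, peritoneal dialysis | 5 |
| Foetal or neonatal | Foetal renal impairment, neonatal anuria, renal failure neonatal, renal impairment neonatal | 4 |
| Urine output | Anuria, oliguria | 2 |
| Azotaemia | Azotaemia | 1 |

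Total: 7 + 5 + 4 + 2 + 1 = 19.

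**Step 2: search for the missing concepts.** A search of the 19 terms for glomerular, GFR, filtration rate, creatinine, clearance, chronic, decreased, increased and worsen finds 0 matches. Azotaemia is the nearest to a creatinine term.

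**Step 3: follow an AE worded as decreased eGFR, increased creatinine or worsening CKD through the planned outputs.**

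| Output | Built from | Is the event there? |
|---|---|---|
| Renal AE/SAE/DAE and by-term tables, SAP 4.11.3 | Appendix C terms | No, if coded outside the 19 |
| eGFR-decline and stopping-criteria rows, SAP 4.11.3 | Central values, confirmed at the next central sample (within 14 days; an additional analysis drops the time limit) | As a measurement, if central values meet the threshold; not as an AE |
| Discontinued for renal criteria, SAP 4.11.3 | End-of-treatment CRF page | Yes, if drug was stopped under the criteria; otherwise no |
| General AE, SAE and discontinuation tables, SAP 4.11.2 | All AEs by organ class and preferred term | Yes, under its own term; no pooled renal count |

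The second row does not fully stand in for the first. Protocol Appendix F 2 acts on local and/or central samples. Local eGFR uses creatinine alone, and central eGFR uses creatinine and cystatin C (protocol 8.2.4). A participant stopped on local values need not meet the central criteria. The CRF row should count that discontinuation, but a clinically relevant decline that did not lead to stopping has no CRF row. No planned output gives a per-participant renal AE total that includes these wordings.

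**Step 4: what can be said about size.** Let f be the share of participants with a renal AE whose renal AEs are all coded outside the list. The renal table then shows a share 1 − f of them. The documents do not give f. By assumption, f = 25%, 50% or 75% would leave 75%, 50% or 25% in the table; f could also be close to zero. If true counts in two arms are a and b and f is the same in both, the table shows (1 − f)a and (1 − f)b. The difference becomes (1 − f)(a − b), and the ratio stays a/b.

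**The case against.** The strongest reply is that the scheme is coherent as written. Laboratory change is taken from measured values and clinical events from AE terms, and protocol 8.3.5 steers investigators towards clinical wording. Renal impairment, renal failure, prerenal failure and acute kidney injury are all listed, and the five procedure terms partly cover progression to end stage. The eGFR rows, the follow-up eGFR row and the CRF discontinuation row do not depend on AE wording. SAP 4.11.2 shows every AE, SAE and AE leading to discontinuation by preferred term, with key participant information for the last two groups.

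Much of this stands. A reader might infer that these events vanish from the report; they do not. What is missing is a complete renal AE total. The preference for clinical terms is conditional, an asymptomatic eGFR fall may have no clinical term, and worsening CKD is itself clinical wording that the list lacks.

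It is also fair that the documents do not show how such wordings will be coded, so the loss rests on an assumption about coding.

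A reader might also take the four foetal or neonatal terms (4/19 = 21%) as part of the undercount. They are not. The protocol says "Participant must be 21 years of age or older" and limits women to those of non-childbearing potential, so these terms cannot describe a participant's own event. They add nothing and remove nothing.

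**Conclusion.** The gap is real and modest. None of the 19 terms names a decreased eGFR, an increased creatinine or worsening CKD, and the renal AE/SAE/DAE tables select on those terms. AEs coded to the missing concepts would be left out, and the renal total would be understated by an amount that the documents do not allow one to estimate. This assumes that at least some investigators use such wordings and that coding places them outside the list.

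A stronger reading is tempting: that more events are lost in the arms where AZD9977 lowers eGFR more, so that the comparison is biased towards no difference. The documents do not support it. They give no renal event rate, no rate by dose and no coding data. With equal loss the absolute difference shrinks but the ratio between arms does not change, and nothing shows that the loss is unequal.

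The tables are descriptive (protocol 9.4.5). The primary analysis and the stopping rules are not affected.

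**What to change.** In SAP Appendix C, before any unblinding, including the interim analysis, add to the renal list the preferred terms for decreased glomerular filtration rate, increased blood creatinine, chronic kidney disease and end-stage renal disease, with exact names taken from the MedDRA version in use. In the SAP 4.11.3 renal table, report one participant-level total for AEs, SAEs and DAEs over the whole list. Show laboratory-only terms on a separate line, so that the count under the present 19 terms stays visible. Timing matters because terms added after results by arm are known would look data-driven.

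The cost is one appendix edit and one extra line in a planned table; no new data are needed. The downside is that the total will include some asymptomatic laboratory-only AEs and will overlap in part with the eGFR rows. Deleting the four foetal or neonatal terms is optional tidying and changes no count.
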